Exercise and Weight Loss to Improve Mobility Function in Veterans With PAD

NCT02607033

Version 4/12/2023

Principal Investigator: [name], PT, DPT, PhD

Sponsor or funding source: Department of Veterans Affairs

Peripheral artery disease (PAD) affects an estimated 12 -15 million adults in the US and an estimated 20% of older Veterans. Those with PAD ambulate with slow gait and experience decreased leg strength, dysmobility, reduced quality of life, serious morbidity, and often premature death. It is estimated that over 60% of individuals with PAD are overweight or obese. While PAD itself worsens mobility, obesity adds a further functional burden to older adults with PAD. Individuals diagnosed with PAD, who are also obese typically claudicate 40% more quickly than non-obese individuals and take 20% longer to recover after claudication. Studies of older obese adults without PAD have demonstrated that the combination of exercise and weight loss is more effective at improving physical function and body composition than exercise alone. While these findings likely translate to older adults with PAD, this hypothesis has yet to be tested.

This study is designed to determine whether weight loss and exercise (WL+EX) versus exercise (EX) alone will improve mobility function (walking ability) to a greater extent than exercise alone, and determine the mechanisms underlying changes in mobility function. The investigators hypothesize that a combined intervention of weight loss and exercise (aerobic and restive) will result in greater improvements in mobility function through improved muscle perfusion and reduced muscle fat infiltration than exercise alone in obese Veterans with PAD. The aims of the study are as follows:

Aim 1: To compare the effects of WL+EX vs EX on mobility function in obese Veterans with PAD. The primary outcome will be claudication onset time during a standardized treadmill test.

Aim 2: To determine the intrinsic perfusion and muscle mechanism underlying changes in mobility function brought about by the interventions. The primary mechanistic outcome will be muscle perfusion.

Experimental Design:

Overview: This study is designed to determine whether WL+EX will improve mobility function to a greater extent than EX alone and determine the mechanisms underlying changes in mobility function. We will study men and postmenopausal women with PAD. Participants will be randomized to WL+EX or EX alone. All individuals will be studied at baseline and after 6 months of intervention.

Eligibility criteria include:

Inclusion Criteria:

-BMI >25 kg/m²

-ABI <.90

-Able to participate in a supervised exercise program at the Baltimore VA

-No current plan for surgical revascularization

-Claudication or leg symptoms when walking

Exclusion Criteria:

- Unstable angina or a recent heart attack
- Active cancer
- Diagnosis of dementia on medical record.
- Current foot or leg ulcers
- Already exercise 2x/week or more by self-report

Study Procedures:

The experimental design of this study involves 5 phases completed over 6-7 months (Table 1). Phase 1 involves screening and enrollment. Phase 2 involves baseline testing. Volunteers then will be randomly assigned to EX + WL or Ex (control) (phase 3). Phase 4 consists of 6 months of supervised exercise training. Phase 5 consist of post intervention final research testing.

Table 1: Research Design

	Time Duration	Research Activity
Phase 1	1-3 weeks	Screening & Enrollment
Phase 2	1-3 weeks	Baseline Testing
Phase 3	1 day	Randomization
Phase 4	6 months	EX + WL or EX
Phase 5	1-3 weeks	Post Intervention testing

Subject Screening and Enrollment (Phase 1):

Based on our prior studies, a substantial proportion of potential participants will not qualify for the study (screen failures). Therefore, after written informed consent and HIPAA authorization is obtained, a history and physical exam will be performed to determine the presence of PAD and any contraindications to study participation. As part of this screening process individuals will complete 1) a six-minute walk test with ankle and brachial blood pressures taken before and after the test; and 2) a history and physical exam. If a subject has recently (within the past 3 months) had a history and physical examination as part of another research study already linked to this study, we will use the results of the history and physical exam from the prior study to reduce participant burden.

Baseline Testing (Phase 2):

There may be certain circumstances in which the Principal Investigator or clinical investigative team may choose not to perform some of the research procedures described below. If this occurs, it will be noted in the participant research notes. Participants may also be requested to repeat one or more of the research tests should it be necessary due to a technical error in its performance and/or measurement, an inadequate sample is obtained for analysis, or there was an unforeseen problem with data collection.

1. The tests described below will be supervised by staff clinicians with the assistance of CPR-trained study team members. Subjects will walk on a treadmill at approximately 2mph and grade is increased every 2 minutes until the subject cannot continue. Subjects will wear a mask with a mouthpiece that will collect expired air for measurement of ventilated gasses. Subjects are instructed to report the onset of claudication pain and then to walk if they can endure the pain (at which time the test will end). Heart rate and ECG are monitored continuously; arm and ankle blood pressure are monitored intermittently throughout the protocol using either auscultation or Doppler ultrasound. Exercise tests may be stopped if the subjects indicate they are unable to continue or they experience any of the following: chest pain, dizziness, faintness, fatigue, pallor,

cyanosis, cardiac arrhythmias, or decompensation, or severe hyper- or hypotension (American College of Sports Medicine 2006. Guidelines for Exercise Testing and Prescription 7th ed.).

2. Strength Testing: A) Muscular strength (e.g., leg extension, leg press, and/or leg flexion) will be measured by 1-repetition maximum (1RM) testing on Keiser K-300 air powered machines, a Biomedex strength testing system, or using hand-held strength testing devices. Participants will complete a brief, low-intensity warm-up prior to the test. Participants will be asked to perform exercises against a gradually increasing resistance after each successful exercise repetition until the maximal load is obtained. They may perform multiple trials (typically ~3-7) with a brief rest period between trials. B) Plantar and dorsiflexion will be measured using a hand-held dynamometer or a Biomedex strength testing system. Participants will be properly stabilized to ensure minimal movement artifacts. Additionally, verbal encouragement will be provided during task to encourage maximal volitional contraction.

3. Functional Tests and Questionnaires: The physical performance tests include the Modified Physical Performance Test [standing balance, chair rise, book lift, put on and remove jacket, pick up a penny, turn 360 degrees, 50-foot walk, stair ascent/descent, self-selected gait speed (8-foot walk)], grip strength, and the 6-minute walk. We will also administer questionnaires (attached) including the Walking Impairment Questionnaire (WIQ).

4. Body Composition: Total and regional fat mass, lean tissue mass, % body fat, bone mineral content, and bone density will be determined by dual-energy x-ray absorptiometry (DXA). Computed tomography scans of the abdomen and leg are done to quantify regional fat and muscle distribution. We will also measure body circumferences with a tape measure.

Randomization (Phase 3): Participants are randomly assigned to either EX + WL or EX as described below.

Interventions (Phase 4):

Individuals will be randomly assigned to six months of supervised exercise in one of the interventions below

1. Active Exercise Training: All participants who are in the exercise program will exercise for approximately 6 months, 3 times per week at VA exercise facilities. These exercise sessions will be supervised by exercise physiologists or trained staff. The aerobic exercise training program will include a warmup followed by 30-45 minutes of cumulative walking on a treadmill, around a track, or around their home if home exercise program is utilized. Individuals will initially begin walking for 10-15 minutes per exercise session (depending on tolerance) and will progress weekly until 30-45 minutes of cumulative walking has been achieved. For individuals who experience claudication pain, they will be asked to walk until the claudication pain reaches a 3 on a 0-4 scale (0= no pain, 1 = onset of pain, 2 = moderate pain, 3 = intense pain, and 4 = maximal pain) after which they will rest. They will then be asked to walk again. This pattern of intermittent walking will be continued until the prescribed number of minutes of walking is met. Subjects will also be asked to walk at home on days they do not perform supervised exercise. Participants may also participate in strength training (ST) during the same session. This will consist of training of the knee extensors, knee flexors, plantar flexors and dorsiflexors. Subjects will perform approximately 1-3 sets of 4-15 repetitions for each exercise as tolerated. Training may be performed on Keiser K-300 air powered machines utilizing pneumatic resistance (Leg Extension Machine, Leg Curl Machine, Leg Press Machine) or with resistance bands or tubes. Each session of ST will take approximately 15-30 minutes. Blood pressure and heart rate will be

assessed before and after each session. If the participant has type 2 diabetes and is on medications that may result in hypoglycemia, we will monitor blood glucose levels before and after exercise or educate patient to do so if they are exercising at home.

2. Active Exercise + Weight Loss: Participants with $BMI > 25\text{kg}/\text{m}^2$ may be assigned to a weight loss group. This group will also receive active exercise as described above for 6 months. These participants will be counseled to lose body weight to assess the additive effect of weight loss on study outcomes. These participants will be encouraged to attend weekly weight loss classes where they will receive instructions on how to implement a heart-healthy weight loss diet (250-350 kcal reduction per day). If they are unable to participate in person, this may be done over the phone. During these sessions, participants will learn how to adjust their eating habits, record and weigh what they eat, read food labels to eat low calorie high nutritional value foods low in saturated fat and cholesterol and sugar, develop proper eating behavior at the dinner table, and by following the recommendations for the America Heart Association and including approximately 1g of high-quality protein per kilogram of body weight per day. Participants may be asked to use The ASA24 system (<https://asa24.nci.nih.gov/>) to collect 24-hour food recalls during baseline testing and the intervention to self-monitor progress and document adherence. National Cancer Institute (NCI) investigators created the free, web-based Automated Self-Administered 24-hour Recall (ASA24) system to administered 24-hour recalls. The ASA24 system consists of a Respondent Website, used to collect data from participants, and a Researcher Website for managing study logistics and access nutrient and food group data files. The coordinator or study dietician will log into the VA computer and access the website and subject specific food logs. These subjects may be asked to continue the intervention until at least 5-10% weight loss is achieved.

Post Intervention testing (Phase 5): After six-months of the intervention, testing will be repeated as described in Phase 2.

Statistical Analysis Plan:

We will use exploratory data analyses to review our data looking for extreme values which will be checked for transcription or other errors. Because our outcome measures will be measured multiple times, our intent is to use repeated measures ANOVA to compare outcome measures among treatment (EX + WL) and the active control (EX). However, as this is a pilot study designed to demonstrate proof of concept and to generate data with which to make accurate power calculations, we may initially analyze within-group changes using paired t-tests and among-group differences with independent samples t-tests.

Supporting References

1. Crowther, R.G., et al., Relationship between temporal-spatial gait parameters, gait

kinematics, walking performance, exercise capacity, and physical activity level in peripheral arterial disease. *J Vasc Surg*, 2007. 45(6): p. 1172-8.

2. Gardner, A.W., L. Forrester, and G.V. Smith, Altered gait profile in subjects with peripheral arterial disease. *Vasc Med*, 2001. 6(1): p. 31-4.
3. Gardner, A.W., et al., The effect of claudication pain on temporal and spatial gait measures during self-paced ambulation. *Vasc Med*, 2010. 15(1): p. 21-6.
4. Kuo, H.K. and Y.H. Yu, The relation of peripheral arterial disease to leg force, gait speed, and functional dependence among older adults. *J Gerontol A Biol Sci Med Sci*, 2008. 63(4): p. 384-90.
5. McCully, K., et al., The effects of peripheral vascular disease on gait. *J Gerontol A Biol Sci Med Sci*, 1999. 54(7): p. B291-4.
6. McDermott, M.M., et al., Gait alterations associated with walking impairment in people with peripheral arterial disease with and without intermittent claudication. *J Am Geriatr Soc*, 2001. 49(6): p. 747-54.
7. McGrath, D., et al., Peripheral arterial disease affects the frequency response of ground reaction forces during walking. *Clin Biomech (Bristol, Avon)*, 2012. 27(10): p. 1058-63.
8. Myers, S.A., et al., Gait variability is altered in patients with peripheral arterial disease. *J Vasc Surg*, 2009. 49(4): p. 924-931.e1.
9. Parmenter, B.J., et al., Preliminary evidence that low ankle-brachial index is associated with reduced bilateral hip extensor strength and functional mobility in peripheral arterial disease. *J Vasc Surg*, 2013. 57(4): p. 963-973.e1.
10. Wurdeman, S.R., et al., Patients with peripheral arterial disease exhibit reduced joint powers compared to velocity-matched controls. *Gait Posture*, 2012. 36(3): p. 506-9.

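### The hypothesis and Aim 1 name obese Veterans with PAD, but entry and the weight-loss arm require only BMI above 25, so a conclusion in Aim 1's words would not match the population admitted

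*Combined protocol and SAP*

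**What the plan says.** The opening summary of the combined protocol and SAP states the hypothesis as a greater gain from weight loss plus exercise "than exercise alone in obese Veterans with PAD". Aim 1 repeats that population: "To compare the effects of WL+EX vs EX on mobility function in obese Veterans with PAD".

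The Inclusion Criteria set one BMI threshold, above 25 kg/m². Under Interventions (Phase 4), item 2, participants who meet that same threshold "may be assigned to a weight loss group". No higher cut-off and no definition of obesity appears anywhere.

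The opening summary itself keeps the two categories apart. It says that "over 60% of individuals with PAD are overweight or obese", and it contrasts obese with non-obese patients on how soon claudication begins. Its case for adding weight loss to exercise rests on obese people: "Studies of older obese adults without PAD have demonstrated that the combination of exercise and weight loss is more effective".

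The Statistical Analysis Plan compares the arms by repeated measures ANOVA. Because the study is a pilot, it may first use paired t-tests within groups and compare "among-group differences with independent samples t-tests". It names no BMI subgroup, BMI covariate or obese-only analysis set. One declared purpose of the pilot is "to generate data with which to make accurate power calculations".

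**The concern.** A trial's conclusion should describe the people its entry criteria admit. Here the research question is put for obese patients, the entry rule is put for a BMI range that on the document's own vocabulary also takes in overweight patients, and nothing in the analysis narrows the result back to the obese. If the report answers Aim 1 in Aim 1's words, it will claim a population that the trial did not define.

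The pilot's figures are also meant to be reused. Whoever plans the next trial needs to know which population the effect estimate and the SD describe. If that trial is restricted to obese patients on the strength of Aim 1, its inputs would come from a wider BMI group. The documents do not say whom a later trial would enrol; if it again used BMI above 25, this consequence would not arise.

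**Working it through.** The main point is a comparison of text. The plan states no sample size, alpha, power or effect size, so there is no figure of its own to reproduce.

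**Population, place by place**

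| Place | BMI population |
|---|---|
| Hypothesis | obese |
| Aim 1 | obese |
| Title | BMI not mentioned |
| Experimental Design, Overview | BMI not mentioned |
| Inclusion Criteria | BMI above 25 kg/m² |
| Interventions, item 2 (weight-loss arm) | BMI above 25 kg/m² |
| Statistical Analysis Plan | arms as randomized, no BMI restriction |

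The conflict is between the first two rows and the two BMI rows. One step is an assumption: that BMI above 25 admits people who are not obese. The documents give no obesity cut-off, so this rests on the conventional one (30), supported by the summary's separate use of overweight and obese.

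**Can the effect on the estimate be sized?** Let f be the non-obese share and q the benefit in non-obese participants divided by that in obese participants. With the same mix expected in both arms,

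pooled effect / obese-only effect = 1 − f(1 − q).

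This equals 1 when q = 1, falls below 1 when q < 1 and rises above 1 when q > 1. The documents give neither f nor q. Assumed values of f = 0.30 to 0.60 and q = 0.5 to 1.5 give ratios from 1 − 0.60 × 0.5 = 0.70 to 1 + 0.60 × 0.5 = 1.30. That range is centred on 1 only because the chosen q is. It carries no information about this trial, and I give no size for the mismatch.

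**Separate precision point.** Assumptions: two visits (baseline and 6 months, as the Overview states), equal variances, complete data, and baseline to 6-month correlation r in each arm. The documents give no value for r; I take 0.5 to 0.8. The between-arm variance is then proportional to:

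- final values: 1
- changes: 2(1 − r). With two visits, the arm-by-time test in repeated measures ANOVA is the same test as the t-test on changes.
- 6-month value adjusted for baseline: 1 − r²

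So adjusted / changes = (1 − r²) / [2(1 − r)] = (1 + r)/2, and adjusted / final values = 1 − r².

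| r (assumed) | Adjusted / changes | Adjusted / final values |
|---|---|---|
| 0.5 | 0.75 | 0.75 |
| 0.7 | 0.85 | 0.51 |
| 0.8 | 0.90 | 0.36 |

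The plan does not say whether its independent t-tests use changes or final values, so both columns are needed. The ratios leave out the small inflation from estimating the baseline slope. The sample size is not stated, so I cannot put a figure on it; it matters most where the gain is smallest.

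**The case against.** The best defence is that obese is loose shorthand, made operational by the explicit BMI criterion. Because the documents never define the word, this cannot be ruled out, and on that reading the defect is an undefined term. It does not remove the point. The summary names overweight and obese as two categories and uses non-obese as a contrast, so the shorthand would conflict with the document's own usage, and the same rewording would be needed. The criteria are introduced as a list that may not be complete, but no other BMI rule appears.

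A reader might go further in three ways that the documents do not support.

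- *The comparison is biased or invalid.* It is not. Both arms share the same entry rule, and randomization protects the contrast in whoever is enrolled. Only the label on the population is affected.
- *Overweight participants dilute the effect.* The summary says obese patients with PAD reach claudication 40% sooner than non-obese patients. That concerns the level of the outcome, which is the primary one. It does not show that the benefit of added weight loss varies with BMI, in either direction.
- *The Overview gives a third, conflicting population.* Its sentence "We will study men and postmenopausal women with PAD" concerns sex and menopausal status, is silent on BMI and is compatible with either reading.

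It is also fair to object that the documents do not show which population was intended, so rewording the aim is a choice. That stands. I prefer it because it leaves enrolment alone. Finally, baseline adjustment has no bearing on the mismatch and should not be read as evidence for it.

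**Conclusion.** The mismatch is in the current text and can be stated with high confidence: the hypothesis and Aim 1 say obese, while entry and the weight-loss arm say BMI above 25, and no planned analysis recovers the narrower group. The randomized comparison answers the question for the patients admitted, and a conclusion in Aim 1's words would overstate how specific that answer is to obesity. Severity is minor. If the benefit of weight loss does not vary with BMI, only the wording is wrong; if it does, neither the size nor the direction of the gap can be derived from the documents.

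The word Veterans needs the same care. It stands in the title, the hypothesis and Aim 1, but the listed criteria ask only that a person can take part in supervised exercise at the Baltimore VA. They do not require Veteran status.

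The precision gain from baseline adjustment is a separate, smaller improvement. Its size depends on the assumed correlation and on complete data at both visits.

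**What to change.** Leave eligibility, enrolment, randomization and visits as they are, and reconcile the text:

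1. State the hypothesis, Aim 1 and the reported conclusion for patients with PAD and BMI above 25 kg/m² (overweight or obese). Use Veterans only if Veteran status is in fact an entry requirement; if it is, add it to the listed criteria.
2. Report the baseline BMI distribution by arm, so that a reader or the planner of a later trial can see whom the estimates describe.

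If the investigators did mean obese patients only, the alternative is to define the term and pre-specify an analysis of that subset, accepting fewer participants in a pilot whose size is not stated.

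The cost is a few words and one row in the baseline table, plus a dated amendment if recruitment has begun. The claim becomes less specific to obesity.

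Separately, specify the between-arm comparison in the Statistical Analysis Plan as a linear model of 6-month claudication onset time on arm and baseline value. The baseline value is already collected, so the price is one degree of freedom. This improves precision and does not replace items 1 and 2.

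### The only glucose-check rule is limited to type 2 diabetes, so an enrolled insulin user with another type has no required checks or home self-check education

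*Combined protocol and SAP*

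**What the plan says.** Under Interventions (Phase 4), item 1 (Active Exercise Training), the protocol states: "If the participant has type 2 diabetes and is on medications that may result in hypoglycemia, we will monitor blood glucose levels". Two conditions must both hold: the participant has type 2 diabetes, and takes a medicine that can lower glucose too far. For those who meet both, the checks fall on either side of each bout of exercise, and teaching the participant to self-check takes their place when the exercise is done at home.

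The same item says of the training sessions: "These exercise sessions will be supervised by exercise physiologists or trained staff". It requires blood pressure and heart rate before and after each session for everyone. It also sets an expectation for the other days: "Subjects will also be asked to walk at home on days they do not perform supervised exercise". A home exercise program is allowed as well.

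The entry criteria, in the Overview under Experimental Design, open with "Eligibility criteria include" and list five inclusion and five exclusion items. Subject Screening and Enrollment (Phase 1) adds that "a history and physical exam will be performed to determine the presence of PAD and any contraindications to study participation".

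**The concern.** The hazard that the rule names comes from the medicine. Protection, however, also depends on the type of diabetes. An insulin-treated participant with type 1 or another non-type-2 form faces the hazard the rule was written for, yet the sentence read literally gives that person neither the checks nor the education.

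What is at stake is participant safety, mainly on home-walking days. At the facility, trained staff are present. At home the protocol describes no staff presence, and self-check education is the one stated measure against hypoglycaemia. That measure has the same type 2 limit.

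**Working it through.** The plan gives no figure to reproduce on this point. The check is a reading of the whole text, followed by a simple exposure count.

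**1. Is there another glucose rule?** The text was read for diabetes, glucose, insulin and hypoglycaemia.
- Item 1 of Phase 4 holds the only rule.
- The only other mention of diabetes is in the title of reference 32, which sets no rule.
- The stopping criteria in Baseline Testing (Phase 2), item 1, list signs such as dizziness, faintness and pallor. They govern the exercise tests, and glucose is not among them.
- Item 2 of Phase 4 (Active Exercise + Weight Loss) prescribes a daily reduction of 250-350 kcal, with no glucose or medication rule attached.

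**2. Can a participant with another diabetes type enter?**
- Inclusion: BMI, ABI, ability to take part in supervised exercise, no planned surgical revascularization, and "Claudication or leg symptoms when walking". That is 5 items, 0 of which mention diabetes.
- Exclusion: unstable angina or recent heart attack, active cancer, dementia, foot or leg ulcers, and "Already exercise 2x/week or more by self-report". That is 5 items, 0 of which mention diabetes or insulin.
- Total: 5 + 5 = 10 criteria, 0 on diabetes.

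The list may not be exhaustive, and the screening examination looks for contraindications. Entry is therefore not excluded by the listed criteria, rather than expressly allowed. The protocol treats type 2 diabetes with such medicines as something to monitor, not as a bar to entry, so the examination cannot be assumed to remove every insulin user of another type.

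**3. What is required for each participant on such a medicine?**

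| | Type 2 diabetes | Another diabetes type |
|---|---|---|
| Staff supervision at sessions | yes | yes |
| Blood pressure and heart rate at sessions | yes | yes |
| Glucose before and after exercise | yes | not required |
| Self-check education for home exercise | yes | not required |

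**4. Nominal exposure for one such participant.** Inputs: 3 supervised sessions per week (item 1 of Phase 4); 26 weeks (assumed, for approximately 6 months); full attendance (assumed); walking on every other day (assumed, as an upper limit).
- Supervised sessions: 3 × 26 = 78.
- Home-walking days: (7 − 3) × 26 = 4 × 26 = 104 at most.

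Use of the home program would move sessions from the first count to the second. In the weight-loss arm the intervention may be continued until at least 5-10% of weight is lost, so exposure could be longer there.

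**The case against.** The strongest reply is that the gap needs a participant whom the documents never show. They give no diabetes share of any type and no sample size, and the Statistical Analysis Plan calls this a pilot study. The affected group may be empty. In addition, the criteria list is open-ended, screening can take account of diabetes type and insulin, and the rule is a minimum: staff may check anyone's glucose. This stands as a limit on the size of the problem. It does not close the gap. Screening judgement is discretion, not a glucose rule, and staff discretion at the facility does not reach home walking. The protocol also added glucose checks for type 2 participants despite the same supervision, so it does not itself treat supervision as enough.

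A second reply is that the exposure counts describe anyone's schedule and do not measure harm. That is correct. They show only how often the missing requirement would apply to one person, and the 104 is an upper limit because the protocol fixes no number of home walks.

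A third is that, if the medicine is the hazard, the condition should be the medicine alone. This is a fair drafting point. It would broaden the fix, but widening to any diabetes type already covers the case described.

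**Conclusion.** The concern holds. The protocol states a safety rule whose scope is narrower than the hazard it names, and nothing else in the visible text fills the gap. The number of people affected is unknown, probably small and possibly zero. For one such participant the nominal exposure is 78 supervised sessions and up to 104 home-walking days, under the assumptions of 26 weeks, full attendance and a walk on every unsupervised day.

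The conclusion rests on reading the sentence literally and on such a person passing the screening examination. It does not claim that staff are barred from checking, or that harm is expected. Both arms follow the same exercise rule, and the primary outcome and the comparison between arms are untouched. The change should be made because it is cheap and protects participants, but it is not a flaw that undermines the trial.

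**What to change.** In the glucose sentence of Interventions (Phase 4), item 1, replace the words *type 2 diabetes* with *diabetes of any type*. Keep the medicine condition and the rest of the sentence, so that both the checks and the home self-check education extend to everyone with diabetes on such a medicine. Leave the eligibility criteria as they are.

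The cost is one edited phrase, plus glucose checks and brief education for any participant newly covered. If no such participant enrols, the edit is the whole cost. Eligibility, endpoints and analysis do not change.

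### With one baseline and one post-intervention test, the primary Aim 1 comparison should carry baseline claudication onset time as a covariate (ANCOVA) rather than rest on repeated measures ANOVA

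*Combined protocol and SAP*

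**What the plan says.** Aim 1 names claudication onset time on a treadmill test as the primary outcome. The Experimental Design overview sets two occasions: "All individuals will be studied at baseline and after 6 months of intervention". The Phase 5 text agrees: "After six-months of the intervention, testing will be repeated as described in Phase 2". The baseline treadmill test already captures the outcome: "Subjects are instructed to report the onset of claudication pain".

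The Statistical Analysis Plan is one paragraph. Its reason for the chosen method is "Because our outcome measures will be measured multiple times", and the method is "our intent is to use repeated measures ANOVA to compare outcome measures among treatment (EX + WL) and the active control (EX". It then allows a simpler start: "we may initially analyze within-group changes using paired t-tests and among-group differences with independent samples t-tests". The reason given is that "this is a pilot study designed to demonstrate proof of concept and to generate data with which to make accurate power calculations".

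No section mentions ANCOVA, a baseline covariate or any other baseline adjustment. The plan does not say which ANOVA term is the treatment test, or whether the independent samples t-tests use six-month values or changes.

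**The concern.** Under this schedule, being measured multiple times means being measured twice. With two arms and two visits, repeated measures ANOVA has nothing to model beyond each participant's change, so its group-by-time test fixes the slope of post on baseline at 1. A t-test on six-month values, which the plan neither specifies nor excludes, would ignore baseline altogether. Neither lets the data determine how much of the six-month value baseline predicts.

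In a self-described pilot, the arm difference and its confidence interval can reasonably be read as the main product of Aim 1, and precision is scarce. ANCOVA can narrow that interval using data already scheduled for collection. No bias is alleged, and the SDs and correlation needed for later power calculations can be taken from the data whichever test is used.

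**Working it through.** **Inputs.** From the documents: two randomised arms, a continuous outcome, two occasions. The documents give no sample size, alpha, power, SD, correlation or allocation ratio, so there is no stated figure to reproduce. Assumed: baseline-to-post correlation r of 0.3 to 0.8; post/baseline SD ratio s of 0.8 to 1.5; equal allocation; the same r and s in both arms; complete, uncensored data; two-sided 5% tests.

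**Step 1: what the ANOVA tests.** In a simulated data set with two arms and two visits, the group-by-time F was 6.7611 and the squared t on change scores was 6.7611. They are the same test. The group main effect would average baseline into the outcome and is not a sensible treatment test.

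**Step 2: large-sample variances** (baseline variance set to 1):

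- ANCOVA: s²(1 − r²)
- Change score: 1 + s² − 2rs
- Six-month value only: s²

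Change minus ANCOVA is 1 − 2rs + r²s² = (1 − rs)², which is never negative and is zero only when rs = 1. Six-month-only minus ANCOVA is r²s².

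Example, s = 1 and r = 0.5: ANCOVA 1 − 0.25 = 0.75; change 1 + 1 − 1 = 1.00; ratio 0.75.

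**Step 3: against the intended test.** Each cell gives the ANCOVA/change variance ratio and, in brackets, change-score power where ANCOVA has 80%. Power is Φ(2.80 × √ratio − 1.96), with 2.80 = 1.96 + 0.84.

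| s | r = 0.3 | r = 0.5 | r = 0.6 | r = 0.7 | r = 0.8 |
|---|---|---|---|---|---|
| 0.8 | 0.50 (51%) | 0.57 (56%) | 0.60 (58%) | 0.63 (60%) | 0.64 (61%) |
| 1 | 0.65 (62%) | 0.75 (68%) | 0.80 (71%) | 0.85 (73%) | 0.90 (76%) |
| 1.25 | 0.78 (70%) | 0.89 (75%) | 0.94 (78%) | 0.98 (79%) | 1.00 (80%) |
| 1.5 | 0.87 (74%) | 0.96 (79%) | 0.99 (80%) | 1.00 (80%) | 0.95 (78%) |

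At s = 1, the extra participants a change-score test needs are 1/ratio − 1: 54% at r = 0.3, 33% at 0.5, 11% at 0.8.

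**Step 4: against a six-month-only t-test.** The ratio is 1 − r² at any s: 0.91, 0.75 and 0.36 at r = 0.3, 0.5 and 0.8, giving 76%, 68% and 39% power where ANCOVA has 80%.

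**Step 5: small-sample cost.** Estimating the slope multiplies ANCOVA variance by 1 + 1/(2n − 4), with n per arm: 1 + 1/16 = 1.063 at 10, 1 + 1/36 = 1.028 at 20, 1 + 1/56 = 1.018 at 30. ANCOVA therefore has the larger variance only where the Step 2 ratio exceeds 0.941, 0.973 or 0.982.

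**Step 6: simulation** (normal data, 40,000 runs per cell, effect set for 80% large-sample ANCOVA power). ANCOVA against change-score power at 10 per arm: 73% v 47% (s = 0.8, r = 0.3); 73% v 63% (s = 1, r = 0.5); 73% v 75% (s = 1.25, r = 0.8); 73% v 76% (s = 1.5, r = 0.7). At 20 per arm: 77% v 71% (s = 1, r = 0.7). At 30 per arm: 78% v 74% (s = 1, r = 0.8). Over the whole grid the difference runs from +26 to −3 points at 10 per arm, and from about +28 to −1 at 20 and at 30. Under the null, each test rejected in 4.8% to 5.3% of runs.

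**The case against.** The strongest reply is that nothing planned is invalid. The change-score test is unbiased under randomisation, the pilot's stated purpose is served by either analysis, and the benefit in this trial is unknown. The 80% power comparisons describe a hypothetical trial. Both arms exercise for six months; if the spread of onset times widens as times lengthen, s exceeds 1 and the gain falls to 0 to 5 points for r of 0.5 to 0.8. All of that stands, and it limits the point to one of efficiency.

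Two technical limits also stand:

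- **Very small trials.** The sample size is unstated and could be below 10 per arm. Variance inflation is 1 + 1/6, or 17%, at 5 per arm and 1 + 1/12, or 8%, at 8. In simulation, ANCOVA at 5 per arm lost in 10 of the 20 grid cells, by up to about 7 points; at 8 per arm the worst loss was about 4.
- **Unequal allocation with different slopes.** The variance ordering in Step 2 needs equal allocation or a common slope. With 2:1 allocation, slopes of 1.5 and 0.5, and unit baseline and residual variance, the pooled slope is (2 × 1.5 + 0.5)/3 = 1.17. With m in the smaller arm, ANCOVA variance is 1.11/(2m) + 1.44/m = 2.00/m, against 1.25/(2m) + 1.25/m = 1.875/m for change scores, about 7% larger.

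These are edge cases. They qualify the claim but do not favour the planned test in general: r and s are unknown in advance, and at 10 or more per arm the possible gain far exceeds the possible loss.

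**Conclusion.** The concern holds as a recommended improvement, not as a correction of an invalid test. The design has one baseline and one post-intervention value, the intended ANOVA reduces to change scores, and no baseline covariate is planned. With equal SDs, ANCOVA cuts variance by 10% to 25% at r of 0.5 to 0.8 and by 35% at r = 0.3. The large-sample gain is nil where rs = 1. These sizes rest on assumed r and s, equal allocation, a common slope, complete uncensored data and about 10 or more participants per arm.

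Two matters lie outside this point and ANCOVA cures neither. One is how an unobserved onset time is handled. The other is the statement under the weight-loss intervention that "These subjects may be asked to continue the intervention until at least 5-10% weight loss is achieved", which could shift the test date in one arm only.

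**What to change.** In the Statistical Analysis Plan, state that the primary Aim 1 comparison is post-intervention claudication onset time by randomised arm, with baseline claudication onset time as a covariate, reported as an adjusted difference with a 95% CI. Participants should be analysed as randomised. A two-visit mixed model with baseline means constrained equal across arms is an alternative that gives essentially the same answer with complete data. Label the repeated measures ANOVA and the independent samples t-tests as supportive, and the within-arm paired tests as descriptive.

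The cost is one or two sentences and one degree of freedom; no new data are needed. The downside arises when rs is near 1: about 2 to 3 points of power at 10 per arm and about 1 at 20 or 30. If recruitment could fall well below 10 per arm, the loss can be larger.
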